6.4.3 Safety Population

The safety population is defined as all subjects who were administered FCX-007. All safety analyses will be performed using the safety population.

6.5 Demographic and Other Baseline Characteristics

All baseline summaries will be done on the FAS and safety populations.

Sex, race, and ethnicity will be summarized by counts and percentages. Age, height (in), and weight (lbs.) will be summarized with descriptive statistics. Also, disease measures such as

mutation, baseline COL7 IF and EM characteristics if applicable, and antibody presence will be summarized.

Genetic testing results will be presented in listings. Vital signs collected at screening will be summarized with descriptive statistics.

Medical histories will be coded using the MedDRA dictionary and presented in a by-subject listing.

6.6 Prior and Concomitant Medications

Prior and concomitant medications will be coded to preferred name and Anatomical Therapeutic Chemical (ATC) classification of ingredients using the World Health Organization (WHO) Drug dictionary (WHO-DDE). Counts and percentages will be provided to summarize the use of medications reported throughout the study. The number and percent of subjects who took medications will be shown by ATC level 2 term and preferred name. Medications which start prior to first injection will be considered prior medications. Ongoing medications and medications ending after the date of first injection will be considered concomitant medications. Medications which are both prior and concomitant will be included in summary. Incomplete start and end dates which could be either prior to first injection or after first injection will be considered prior to first injection.

A by-subject listing of all prior and concomitant medications will be presented.

6.7 Analysis of Efficacy

6.7.1 Primary Efficacy Analysis

The primary efficacy endpoint is complete wound closure of the First Wound Pair at Week 24, with confirmed complete wound closure at serial assessments at Weeks 22 and 24. The number and percentage of complete closures will be reported by treatment group.

The primary efficacy analysis will be presented for the FAS population.

6.7.2 Secondary Efficacy Analysis

For all secondary endpoints, numbers and percentages of complete closures will be reported by treatment group.

The secondary efficacy analysis will be presented for the FAS population.

6.7.3 Supportive Efficacy Analysis

Durability of wound closure from Week 24 through Week 48 is defined as a wound assessed as closed at Week 24 (with confirmatory closure at Week 22), as well as closed at the Week 36 and Week 48 WA. Summaries will be done for both First wounds and all qualifying wounds (those assessed as closed at Week 24) by treatment group.

Durability of wound closure from Week 24 through Week 36 is defined as a wound assessed as closed at Week 24 (with confirmatory closure from Week 22), as well as closed at the Week 36 WA. Summaries will be done for both First wounds and all qualifying wounds (those assessed as closed at Week 24) by treatment group.

Durability of wound closure from Week 12 through Week 48 is defined as a wound assessed as closed at Week 12, as well as closed at Weeks 24 (with confirmatory closure at Week 22), 36 and 48 WAs. Summaries will be done for both First wounds and all qualifying wounds (those assessed as closed at Week 12) by treatment group.

Durability of wound closure from Week 12 through Week 36 is defined as a wound assessed as closed at Week 12, as well as closed at Weeks 24 (with confirmatory closure at Week 22) and 36 WAs. Summaries will be done for both First wounds and all qualifying wounds (those assessed as closed at Week 12) by treatment group.

The Wong-Baker FACES Pain Rating Scale will be summarized by visit with changes from Baseline at Weeks 12, 24, 36 and 48. Summaries will be done for the First wound pair, and all wound pairs, as well as by maximum across wounds (treated and control).

COL7 expression in treated wounds as assessed by IEM and IF at Weeks 36 and 48 will be presented in listings.

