10.4. PLANNED ANALYSES

This section briefly describes the planned statistical analysis. A Statistical Analysis Plan (SAP) will be written that provides specific details of these analyses and will be finalized prior to database lock. In case the language in this section differs from the language in the SAP, the SAP is considered operative.

Statistical analyses will be performed using 2-sided tests at a Type I error rate of 0.05. The secondary outcomes will only be formally tested if the primary outcome is statistically significant.

Data will be summarized by treatment regimen and, when applicable, by study visit. Descriptive statistics including counts and percentages for categorical data; and n (number of subjects), mean, standard deviation (SD), median, minimum and maximum for continuous data will be presented for each evaluable parameter for change from baseline as well as the value at each timepoint. For discrete variables, descriptive analyses will be based on numbers of subjects and related percentages.

The SAP will specify the details of the analyses to be used for the efficacy, safety, and supportive analyses, including methods for missing data. All data listings, summaries, figures, and statistical analyses will be generated using SAS version 9.4 or higher or other validated software.

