7. DETERMINATION OF SAMPLE SIZE

The originally planned sample size was based on observed Phase 1/2 study data, 60% wound closure in treated wounds, and 10% wound closure in control wounds is assumed, with a total discordance of 70%. A sample size of 24 would have provided 85% power at a significance level of 0.05 to detect a difference of 50% between treated and control wounds when there are 70% discordant pairs, using a McNemar's test. All calculations were performed with PASS 2020 v20.0.2.

However, due to limitations in manufacturing lentiviral vector required for manufacturing FCX-007, the sample size was limited to 6 enrolled subjects.

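### SAP 6.7.3 sets durability side by side by arm in wounds selected by closure after randomisation, leaves the First-wound denominator unstated, and for the Week 24 endpoints lets unconfirmed closures into the qualifying set

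*SAP*

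**What the plan says.** SAP 6.7.3 defines four durability endpoints. Durability from Week 24 through Week 48 "is defined as a wound assessed as closed at Week 24 (with confirmatory closure at Week 22"), together with closure at Weeks 36 and 48. The Week 24 to 36 version drops the Week 48 condition. For both of these the reporting rule is: "Summaries will be done for both First wounds and all qualifying wounds (those assessed as closed at Week 24) by treatment group".

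The two endpoints that start at Week 12 require closure at Week 12, confirmed closure at Week 24, and closure at Week 36 (and Week 48 for the longer one). Their reporting rule has the same form, with qualifying wounds being those closed at Week 12.

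No sentence in 6.7.3 names a denominator. The parenthesis follows the words about qualifying wounds, so it does not settle whether the First-wound summary covers all First wounds or only the closed ones.

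The primary endpoint in SAP 6.7.1 uses closure confirmed at Weeks 22 and 24. SAP 6.1 and 8 make the analysis descriptive, and SAP 7 limits enrolment to 6 subjects.

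**The concern.** There are three problems in one rule.

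- **Selection.** Randomisation balances the two wounds of a pair at Day 1. It does not balance the treated wounds that later close against the control wounds that later close. A durability percentage taken within closed wounds and laid out by arm looks like a treatment comparison, but it compares two differently selected sets. This applies to all four endpoints.
- **Mismatch.** For the two Week 24 endpoints, a wound open at Week 22 and closed at Weeks 24, 36 and 48 belongs to the qualifying set as worded, yet fails the durability definition from the start.
- **Unstated denominator.** If First wounds means closed First wounds, the control set may well be empty. If it means all First wounds, the two summaries in the same sentence rest on different bases and cannot be compared.

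Four of the seven supportive endpoints are durability endpoints. In a six-subject trial without tests, the printed counts and percentages are the result, so the denominator decides what a reader takes away.

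**Working it through.** **Inputs**
- Closure rates (SAP 7): "60% wound closure in treated wounds, and 10% wound closure in control wounds is assumed".
- Discordance (SAP 7): "with a total discordance of 70" per cent.
- Planned size (SAP 7): "A sample size of 24 would have provided 85% power at a significance level of 0.05", by McNemar's test. Sidedness (Protocol 10.4): "Statistical analyses will be performed using 2-sided tests at a Type I error rate of 0.05".
- Actual size: 6 enrolled subjects (SAP 7). One to three wound pairs per subject (Protocol 7.1 and 8.3.1.2), hence 6 to 18 control wounds if all 6 subjects are in the FAS.

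**1. The plan's own figure.** The plan states no figure for durability; the only one to reproduce is the power. With 60% and 10% closure, discordance = 60 + 10 − 2 × (both closed), so 70% means that no pair closes on both sides. I summed the exact two-sided McNemar test over the number of discordant pairs, Bin(24, 0.70), with split 0.60/0.70. The power is 0.851, which matches 85%. (The uncorrected chi-square version gives 0.899, the continuity-corrected one 0.828.) The 60% and 10% rates are therefore used below.

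**2. Size of the closed First-wound sets with 6 pairs**
- Expected closed: treated 6 × 0.6 = 3.6; control 6 × 0.1 = 0.6.
- P(no control wound closed) = 0.9^6 = 0.531.
- P(at most one) = 0.531 + 6 × 0.1 × 0.9^5 = 0.531 + 0.354 = 0.886.
- P(no treated wound closed) = 0.4^6 = 0.004.
- Sensitivity to the control rate: at 5%, 0.95^6 = 0.735; at 20%, 0.8^6 = 0.262.

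**3. Size of the closed control set across all wounds, at 10%**

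| Control wounds | P(none qualifies), independent wounds |
|---|---|
| 6 | 0.531 |
| 12 | 0.9^12 = 0.282 |
| 18 | 0.9^18 = 0.150 |

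If wounds within a subject always behave alike, the value is 0.531 whatever the number of pairs.

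**4. Numerator against qualifying set, Week 24 endpoints**
- Success: closed at Weeks 22, 24 and 36 (and 48). Literal qualifying set: closed at Week 24.
- If a share u of Week 24 closures was open at Week 22, the highest attainable percentage is 1 − u. The documents give no value for u; assumed values of 10%, 30% and 50% cap durability at 90%, 70% and 50%.
- With four qualifying wounds, of which one is unconfirmed: 3/3 = 100% becomes 3/4 = 75%; 2/3 = 67% becomes 2/4 = 50%; 0/3 and 0/4 are both 0%. The loss is up to 25 points.
- Such wounds are plausible. Recurrent wounds are eligible (Protocol 7.1), and SAP 2 says that most of them heal within about 3 weeks and re-open within about 3 weeks. The Week 22 assessment falls 11 to 21 days before Week 24 (Protocol Table 3).
- The Week 12 endpoints have no such mismatch: closure at Weeks 22 and 24 is part of the outcome there.

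**5. Does an all-wound denominator survive the later treatment of control wounds?** Only unclosed control wounds may be injected at Weeks 24 and 36 (SAP 4.1). All four definitions require closure at Weeks 24 and 36, so a control wound unclosed at either visit has already failed. Later injection cannot turn it into a success.

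**The case against.** The best defence is that 6.7.3 is loosely worded rather than wrong. The sentence just before the reporting rule ties Week 24 closure to Week 22, and the primary endpoint does the same, so closed at Week 24 may be shorthand for confirmed closure. Durability among wounds that closed is also an ordinary descriptive question. Nothing is tested, and confirmed Week 24 closures are reported by arm elsewhere, so a reader could put the durable count over all First wounds. An all-wound figure also partly repeats the closure result.

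Much of this stands, and it rules out stronger readings that a reader might infer:
- *Durability is summarised only among wounds closed at Week 24.* The text does not say so. The First-wound summary may cover all First wounds, and two endpoints use Week 12.
- *The rule gives a wrong figure.* It does so only on the literal reading, and only for two of the four endpoints.
- *The control result will usually be 0/0.* The 0.53 applies to First wounds restricted to closed ones. With 12 or 18 independent control wounds it is 0.28 or 0.15.
- *FCX-007 will look less durable than standard of care.* An invented case can produce this. Let half the wounds be easy (closure 90% treated, 20% control; durability 80%) and half hard (closure 30% and 0%; durability 30%). Among closed wounds, treated durability is (0.5 × 0.9 × 0.8 + 0.5 × 0.3 × 0.3)/0.6 = 67.5%, against 80% for control; over all wounds it is 40.5% against 8%. But none of these values comes from the documents. If both wounds of a pair are of one type and close independently given type, both close in 0.5 × 0.9 × 0.2 = 9% of pairs, so discordance is 60 + 10 − 18 = 52%, not the SAP's 70%.

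What the defence does not remove: the denominator is unstated, the qualifying definition omits Week 22, and a set selected by outcome is presented by arm.

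**Conclusion.** The concern holds in a limited form. The by-arm percentages among qualifying wounds are not a randomised comparison for any of the four endpoints. The Week 22 mismatch affects the two Week 24 endpoints if the text is applied literally. The chance of an empty control set is 0.53 for closed First wounds (0.74 to 0.26 for control rates of 5% to 20%) and 0.15 to 0.53 across all wounds at 10%.

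These figures assume that all 6 enrolled subjects are in the FAS and that the design rate applies to the qualifying set. Closure at Week 24 alone may be more common than 10%, and the documents give no separate rate for Week 12. The 0.15 and 0.28 also assume independent wounds.

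The direction of any selection bias cannot be known from the documents. No formal inference is affected, because the endpoints are supportive and untested. What is at stake is whether the printed durability figures can be read correctly.

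**What to change.** In SAP 6.7.3, for all four durability endpoints:

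1. Report durable closure as number and percentage of all FAS First Pair wounds by arm, and likewise for all analysed wound pairs. Each arm then has up to 6 First wounds, and closure status no longer decides who is counted.
2. Keep the conditional percentage as a within-arm description, always with its numerator and denominator, and say that it is not a comparison between arms.
3. For the two Week 24 endpoints, define qualifying as closed at both Week 22 and Week 24.
4. Show not estimable when no wound qualifies.

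The cost is a few lines of SAP text and one changed denominator in the tables; no new data are needed. The downside is that the stated durability percentages become smaller and partly reflect the closure rate, which is why the conditional summary is worth keeping beside them.

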Details of the clinical photography procedures will be contained in the Study Procedures Manual.

Figure 3: Target Wound Markings – Tattoos**8.3.3. Wong-Baker FACES® Pain Assessment**

The Wong-Baker FACES Pain Rating Scale was originally created for children to communicate about the level of their physical pain, but is now used with people ages 3 and older. The Wong-Baker FACES Pain Rating Scale will be administered to all subjects ages 3 years and older on Day 1 (Visit 2), at the time points indicated in the Schedule of Events (Table 3) **prior to any potential disruption of the target wounds** (i.e., surgical pen markings, target wound tracing, bacterial culture of wounds if applicable, FCX-007 administration preparation or administration, or collection of biopsies). While the scale is designed and validated for general physical pain, each subject will be instructed in the use of the scale and will select a face that illustrated the pain they are experiencing in each identified treatment and control wound.

The Wong-Baker FACES Pain Rating Scale is provided in Appendix 2.

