Subjects will receive intradermal injections of FCX-007 in each specified treatment wound in two or more treatment sessions. Intradermal injections of FCX-007 0.25 mL per linear cm are administered around, and within 1 cm of, the perimeter and across each applicable wound bed; a maximum of 15 mL (in 60 injections) may be administered per session, and the Investigator is encouraged to administer the full quantity of FCX-007 should the total wound size permit. As the wound size and shape will dictate the quantity of FCX-007 to be administered, it is not possible to calculate this until after randomization. As a general rule, the maximum number of injections of FCX-007 is expected to be used over a surface area of approximately 60- 80 cm².

[figure not shown]
The first treatment session occurs at Day 1 (Visit 2) and the second at Week 12/Month 3 (Visit 3). At these visits, the treatment wound in the First Pair will be injected first, followed sequentially by the Second and Third Pairs (if applicable, and only as sufficient product is available). It is permissible for a treatment wound in the Second or Third Pair to be partially treated due to insufficient quantity of product, if the treatment wound in the First or Second Pair was completely treated.

At selected sites only, in a subset of subjects that consent to additional research skin biopsy collection, an additional single treated wound (not from a target wound pair) may be injected with FCX-007 at Day 1 (Visit 2) and Week 12/Month 3 (Visit 3) only.

Additional treatment sessions may occur at Week 24/Month 6 (Visit 4) and Week 36/Month 9 (Visit 5) when unclosed treatment wounds may be re-treated, and unclosed control wounds may be treated.

Safety and efficacy assessments will occur at scheduled intervals through Week 48/Month 12 (Visit 6), when the treatment period is completed, and a long-term safety follow-up period (through 15 years) commences for subjects who have received one or more FCX-007 injections of any volume.

The study schema is presented below.

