6.1.2 Baseline Definition

Baseline is defined as the last non-missing assessment prior to first injection. For the primary endpoint, baseline refers to Day 1 (pre-initial injection) images, measurements and assessments.

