6.4.2 Full Analysis Set (FAS)

All subjects in the randomized population who are administered FCX-007 will be included in the FAS. The primary efficacy analysis will be performed using the FAS.

In the case that a Standard of Care (SOC) wound is inadvertently injected with FCX-007, then the primary efficacy analysis will consider this wound in the SOC group (as randomized) as per the intent-to-treat philosophy.

If any treated wounds from the second or third pairs are not able to be fully treated for any reason, then these wounds will not be included in efficacy analyses beyond the timepoint they were not able to be treated, i.e., Day 1 or Week 12.

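### The change in maximum wound pain can compare different sets of treated wounds at Baseline and follow-up, and so can show a false pain reduction in the FCX-007 arm

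*SAP*

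**What the plan says.** On the pain scale, SAP 6.7.3 states: "The Wong-Baker FACES Pain Rating Scale will be summarized by visit with changes from Baseline at Weeks 12, 24, 36 and 48". It asks for this for the First Pair and for all pairs, "as well as by maximum across wounds (treated and control". It does not say whether that maximum is taken within each arm or over both, or which wounds enter it at each visit.

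The scores are wound-level. Under Protocol 8.3.3 the subject picks a face for "the pain they are experiencing in each identified treatment and control wound", before anything disturbs the wounds. SAP 6.1.2 adds: "Baseline is defined as the last non-missing assessment prior to first injection".

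SAP 6.4.2 contains the exclusion rule. Its condition is: "If any treated wounds from the second or third pairs are not able to be fully treated for any reason". Its consequence is that these wounds "will not be included in efficacy analyses beyond the timepoint they were not able to be treated, i.e., Day 1 or Week 12". The matched control wound is not mentioned. SAP 5.1.3 lists pain as a supportive efficacy endpoint, so the rule reaches it.

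Incomplete treatment is foreseen. SAP 4.1 permits it in the Second or Third Pair when product runs short, and says that "the maximum number of injections of FCX-007 is expected to be used over a surface area of approximately 60- 80 cm²". SAP 6.8.1 plans to report complete versus partial treatment by wound.

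**The concern.** A change in a maximum means something only if both maxima are taken over the same wounds. Here one section defines a maximum without fixing its wound set, and another shrinks the set of treated wounds between Baseline and follow-up. A painful Third-pair wound that is only partly injected on Day 1 can set the baseline maximum and then disappear from every later one. The treated side would show an improvement that no wound experienced, while the control side keeps all its wounds.

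At stake is one descriptive summary of a patient-reported outcome in an open-label trial. No test will be run and enrolment was limited to 6 subjects, so readers will have only the descriptive values to go on.

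**Working it through.** The documents give no figure for this summary, so there is none to reproduce. The check has four steps.

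**Inputs from the documents**
- Scale: six faces scored 0, 2, 4, 6, 8, 10 (Protocol Appendix 2).
- Wounds per arm per subject: one to three (Protocol 8.3.1.2).
- Wound area: about 10 to 50 cm², or 5 to 50 cm² at ages 2 to 6; coverage per session about 60 to 80 cm² (SAP 4.1).
- Subjects: 6 (SAP 7).

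**Assumptions, because the documents give no wound-level pain data**
- Scores are spread evenly over the six faces.
- No wound changes over time.
- Within-subject correlation between wounds is 0.3 to 0.8, with 0 and 1 as limits.

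**Step 1: which scores count when**

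| Treated wound not fully treated at | Baseline | Week 12 | Weeks 24, 36, 48 |
|---|---|---|---|
| Day 1 | in | out | out |
| Week 12 | in | in | out |
| Matched control wound | in | in | in |

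This is the ordinary reading of SAP 6.4.2, with pain scored before injection at each visit.

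**Step 2: direction**

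Let S0 be an arm's wounds at Baseline and Sv the subset left at visit v. With unchanged scores, the artefact is max(Sv) - max(S0), which is at most 0. It is below 0 only if the excluded wound or wounds alone held the maximum.

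Example: three treated wounds score 2, 4 and 8, and the wound scoring 8 is excluded after Day 1. The maximum goes from 8 to 4, a change of -4. Control wounds with the same scores show 0. That one subject moves a six-subject mean by -4/6 = -0.67.

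**Step 3: expected size per affected subject**

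An affected subject is one with an excluded treated wound, whether or not the maximum falls. For k independent, evenly spread scores:

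E[max] = 10 - 2 × Σ (j/6)^k, with j from 1 to 5

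- k = 1: 10 - 2 × 15/6 = 5.00
- k = 2: 10 - 2 × 55/36 = 6.94
- k = 3: 10 - 2 × 225/216 = 7.92

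The differences give the column for correlation 0. The other columns come from a simulation of 400,000 subjects, with correlated normal scores cut into six equally likely faces.

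| Wounds | corr. 0 | 0.3 | 0.5 | 0.8 | 1.0 |
|---|---|---|---|---|---|
| 3 to 2 | -0.97 | -0.80 | -0.67 | -0.42 | 0 |
| 2 to 1 | -1.94 | -1.61 | -1.34 | -0.83 | 0 |
| 3 to 1 | -2.92 | -2.41 | -2.00 | -1.25 | 0 |

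Two other assumed score distributions (one weighted to low scores, one to middle scores), with independent wounds, widen the ranges at correlation 0 to -0.67 to -0.97 (3 to 2), -1.33 to -1.94 (2 to 1) and -2.00 to -2.92 (3 to 1). The maximum falls in 17% to 23% of affected subjects (3 to 2) or 42% to 55% (3 to 1) at correlations 0.8 to 0.3.

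**Step 4: arm mean and the pooled reading**

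One affected subject among 6, at correlations 0.8 to 0.3:
- 3 to 2: -0.42/6 = -0.07 to -0.80/6 = -0.13
- 3 to 1: -1.25/6 = -0.21 to -2.41/6 = -0.40

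If the maximum is instead pooled over all six wounds of three pairs, the shift with independent scores is -0.24 to -0.37 (six to five) or -0.55 to -0.86 (six to four). It is then not a contrast between arms.

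**How likely is an exclusion?** Treatment wounds at the upper size limit total 2 × 50 = 100 or 3 × 50 = 150 cm², above the 60 to 80 cm² of coverage. At the lower limit three total 3 × 10 = 30 cm² (3 × 5 = 15 cm² at ages 2 to 6), well within it. Partial treatment is plausible, but its frequency cannot be read from the documents.

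**The case against.** **The text does not fix the reading.** SAP 6.7.3 does not say the maximum is per arm. SAP 6.4.2 can also be read as removing the wound, rather than its later scores, from any analysis after the failure; the Baseline half of a Week 12 change would then go too, and the artefact would be 0. This objection stands in part. A reader might infer that the plan necessarily creates a false reduction, or always favours FCX-007. The documents support neither: the artefact is possible rather than certain, and it is zero unless the excluded wound alone held the maximum. But the alternative reading is not written down either, and a pre-specified derivation should not depend on which one a programmer chooses.

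**Last observation carried forward could fill the gap.** SAP 6.1 names it for missing efficacy data, while SAP 6.1.5 ties it to the primary and secondary endpoints. It does not help here: an excluded score is present, not missing, and carrying it forward would undo SAP 6.4.2. A reader might go further and infer that any single missing wound score has the same effect in either arm. The documents do not support that, because the carry-forward rule may cover pain, and a filled score leaves the wound set intact.

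**The consequence is small.** Pain is supportive, nothing is tested, comparisons are called exploratory (SAP 6.1.8), and the First Pair summary cannot be touched by this exclusion. Data from all visits are listed and partial treatment is reported, so with 6 subjects a reader could trace a shift. All of this stands and limits the weight of the point. It does not make the summary correct.

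**Conclusion.** The point holds in a conditional form. SAP 6.4.2 and 6.7.3 together allow the treated-side maximum to be taken over fewer wounds at follow-up than at Baseline, with no matching reduction on the control side. On the per-arm reading this can show a false fall in pain with FCX-007 and never, from this exclusion, a false rise; the control arm is unaffected.

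The sizes in steps 3 and 4 of the working rest on assumed score distributions and correlations, apply per affected subject, and vanish at correlation 1. They are not estimates for the trial, because the number of affected subjects is unknown and may be zero. For scale, one face is 2 points. Primary and secondary closure results are not at issue. The sensitivity analysis in SAP 6.7.5 concerns Week 24 closure and does not address this.

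**What to change.** Add to SAP 6.7.3 a definition along these lines: the maximum is computed per subject and visit, separately for treated and control wounds; it uses only wounds that are included and scored at both Baseline and that visit; the baseline maximum is recomputed on that same set; and the same pairs are used in both arms, so that when a treated wound is excluded its matched control wound also leaves this summary.

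With a common wound set the artefact is exactly 0.

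The cost is one sentence in the SAP and a small change to the derivation. A subject's baseline maximum may differ from visit to visit, which needs a table footnote, and some control scores drop out of this summary. Conduct and data collection do not change.
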